Epidemiology, transmission and symptoms

Ever since the first case report in China, the infection has been growing at an accelerating pace and has spread across nearly 213 countries worldwide, infecting over 2.8 million people, resulting 206,018 deaths worldwide (as of 26th April 2020)(6). The reported prevalence ranges from 13% at two medical centers in the United States to 43.5% confirmed cases reported during a joint mission by the World Health Organization at Wuhan province in China.

While a vast majority of cases were categorized as mild or uncomplicated, almost 14% of the patient required hospitalization and/or oxygen support and approximately 5% needed an intensive care admission to survive (7). Common clinical manifestations reported among hospitalized patients were

fever (83-100%), cough (59-82%), myalgia (11-35%), headache (7-8%), and diarrhea (2-10%). All patients had an abnormal radiographic chest imaging (3,8,9).

The two routes by which COVID-19 can be spread is through close contact with an infected person wherein the respiratory secretions are transmitted through the eyes, mouth, nose or airways. The second route of transmission is by touching one's own mouth, nose or eyes after touching the surface, object or the hand of an infected person contaminated with respiratory secretions (10).

National Institutes of Health in the United States has classified the disease severity based on the following symptoms,

Severity	Symptoms
Asymptomatic	Positive test for SARS-CoV-2 but no symptoms
Mild illness	Any signs and symptoms (eg, fever, cough, sore throat, malaise, headache, muscle pain) without shortness of breath, dyspnea, or abnormal chest imaging.
Moderate illness	Evidence of lower respiratory disease by clinical assessment or imaging and a saturation of oxygen (SaO ₂) >93 percent on room air at sea level.
Severe illness	Respiratory frequency >30 breaths per minute, SaO ₂ ≤93 percent on room air at sea level, ratio of arterial partial pressure of oxygen to fraction of inspired oxygen (PaO ₂ /FiO ₂) <300, or lung infiltrates >50 percent.
Critical illness	Respiratory failure, septic shock, and/or multiple organ dysfunction.

COVID-19 and its impact on pregnancy

The obstetrical population is considered vulnerable. Pregnancy involves multiple interactions with the health care system and eventually all are admitted to the hospital for delivery, therefore, managing pregnant population presents a unique challenge during this pandemic. Additionally, the physiological changes and partial immune suppression during pregnancy makes the pregnant women and newborn babies susceptible to several infections. Post-partum hemorrhage, maternal sepsis, preeclampsia, premature rupture of membrane are the most common adverse events reported to have caused by this disease in pregnant women (11).

There are currently limited data on fCOVID-19 infections during pregnancy. Anecdotal evidence suggests that pregnant women do not appear to be different than the general population in terms of disease transmission. In addition, neonatal vertical transmission has been suspected in a neonate of a COVID-19 positive mother (12). Recently, poor maternal and neonatal outcomes including critical care admission, preterm normal and cesarean delivery, premature rupture of the membrane or PROM , fetal distress, stillbirth, and multiple organ dysfunction (1,11,13-17).

Importance of Registry

From the limited information gathered about the novel coronavirus, its impact on pregnancy and newborn and the drastically increasing burden of the disease, it is vital that scientific information concerning the disease is collected and shared in a concise and practical manner. Hence, there is a need to collect case data rapidly, to pool global data on the natural history of women affected by suspected COVID-19 or confirmed SARS-CoV-2 in pregnancy to inform treatment and implement preventative strategies in this and future outbreaks. A centre-based registry, gathering case data prospectively on the effect of SARS-CoV-2 infection from healthcare systems around the world offers a method to accrue clinical outcomes on key research questions from a variety of populations and the Q-PRECIOS register will serve such purpose.

4. Objectives

In this section provide a clear statement of the primary and any secondary objectives of the study

The main aim of this study is to understand the natural course of the COVID-19 infection during pregnancy and postnatal period. To this end the registry objective are to:

1. To form a disease registry linked with other national data sources for women with suspected COVID-19 or confirmed SARS-CoV-2 in pregnancy and their neonates.
 - 1.1 Study the course of COVID-19 disease i.e. its symptoms, duration, progression in pregnant women
 - 1.2 Study the pregnancy, postnatal and neonatal effect of COVID-19 disease

Objective justification

The in-utero exposure of acute viral infection in some instances is proven to have short- and long-term neonatal effect during the postnatal and childhood period and the Zika virus, measles, mumps and rubella are few examples. COVID-19 is caused by a novel coronavirus strain of unknown consequences. The main purpose of this registry is to collect a baseline data and help establishing future studies and hypothesis generation.

In addition, we will be exploring the psychological impact of COVID-19 on women during the pregnancy and postnatal period. Stress and anxiety level are increased with potential adverse pregnancy and/or neonatal outcomes especially during infectious disease outbreak. In fact, COVID-19 is associated with adverse maternal and neonatal outcomes resulting in increased level of stress and anxiety. In addition, women during the pregnancy, peripartum, and postpartum period are at increased risk of depression. A risk that has been aggravated by social and physical isolation. Indeed, the social and physical isolation, a critically needed measure to stop the virus transmission, resulted in increased stress and depression level and adversely affecting the mental and physical health of both the mother and the baby.

5. Indicate if this is a retrospective data review

- **Retrospective Chart/data Review**
- **Provide the date range of the chart review**

6. Study Methodology

This is a nationwide prospective observational registry linked with PAN-COVID UK register of pregnant women with suspected and/or confirmed diagnosis of COVID-19 infection. The enrollment period for this registry is 2 years e.g. May 1, 2020 to May 1st, 2022. Case reports or cases diagnosed ever since 27th Feb will also be included. The authors of published case reports will be contacted for permission. This registry will open for enrollment after IRB/MRC approval. Understanding the effect of COVID-19 infection on pregnancy and its outcome is imperative to help the patients and healthcare providers understand the impact of the disease on the pregnant women and their offspring. There is no intervention planned in this study, therefore, there is a minimal risk associated with this study.

Data collection:

Objective 1: To form a disease registry **linked with other national data sources** for women with suspected COVID-19 or confirmed SARS-CoV-2 in pregnancy and their neonates.

Objective 1.1: Study the course of COVID-19 disease i.e. its symptoms, duration, progression in pregnant women

Objective 1.2: Study the pregnancy and neonatal effect of COVID-19 disease

We will collect information about patient demographic, co-morbidities, clinicopathological information, COVID-19 disease sign, symptoms and its treatment, pregnancy and neonatal outcomes, and women mental health during pregnancy and postnatal period. Regarding pregnancy outcomes, our study will focus on miscarriage, fetal growth restriction and stillbirth, pre-term delivery and vertical transmission and will include fields on ultrasound diagnosis and neonatal care (for details refer to appendix 1, 2 and 3). The woman and her neonate(s) will be followed for 1 year postnatally. Regarding the neonatal outcomes, outlined in the neonatal outcome data collection sheet, includes birth weight, congenital malformations, APGAR score, Breastfeeding, COVID-19 status, respiratory symptoms, neonatal status, and discharge status.

Baseline characteristic and initial assessment will be done during the hospital admission up on COVID-19 diagnosis. Apart from that, there are 7-10 expected follow up telephone calls or online forms to be sent to the patient. The schedule and timeline of data/biospecimen collection are described in table 1.

Data Collection Form or Questionnaire	Baseline	Weekly for 4 weeks	2 nd Trimester (GA 24 weeks)	3 rd Trimester (GA 34 weeks)	GA 36 weeks	GA 38 weeks	6 weeks postpartum	6 Months	12 Months
Demographics, Health History and COVID-19 Questions	X								
COVID-19 Symptoms Follow-up		X	X	X			X	X	X
Pregnancy Status/Outcomes		X	X	X	X	X	X		
Depression and Anxiety*	X		X	X			X	X	X
Neonatal/Infant Outcomes							X	X	X

*Generalized Anxiety Disorder 7-item (GAD-7) scale and Edinburgh Postnatal Depression Scale (EPDS)

7. Study Population and Study Setting/ Location

We will include all pregnant patients with suspected or confirmed COVID-19 infection at all HMC facilities including WWRC, CH, AKH, AWH and its associated quarantine sites and their offspring's. The inclusion criteria are:

1. pregnant woman with suspected or confirmed SARS-CoV-2 infection
2. postpartum women who delivered during the last six weeks and
3. neonate(s) of women included in the registry.

We will also contact corresponding authors of case reports of women with COVID-19 from February 2020 for their written consent, by email, for inclusion of the data from these reports in the PAN-COVID register.

Sample size calculation:

Based on a recently published study, 15% of pregnant women were SARS-CoV-2 positive. Out of which only 12% (1.9% of total study patients) were symptomatic. The total number of deliveries per year in Qatar is between 19000 – 21000 deliveries (1650 patients/month). Diagnosis of COVID-19 in Qatar is based on selective criteria i.e. presenting with symptoms, recent travel to endemic area or contact with a confirmed case. However, all women undergoing cesarean section are screened. Therefore and based on 95% CI and 0.05 margin of error, we anticipate a total 170 - 200 case per month.

8. Study procedures

Study Duration and Timelines

This registry is expected to enroll patients for 2 years and follow them up to 1 year postnatally i.e. the registry duration will approximately last for 4 years.

Study timeline:

Patient enrollment: 2 years

Data collection and curation: 4 years

Study visit numbers: 7-10 visits ([see details below](#)); Initial patient visit is expected to last for 30 minutes.

1. [baseline,](#)
2. [weekly for 4 weeks,](#)
3. [At 24 – 34 – 36 – 38 weeks of gestation \(provided that baseline and the 4 weekly follow up occurred earlier\),](#)
4. [At 6 weeks, 6 and 12 months postpartum \(for both mother and the baby\)](#)

[Further to that, the first visit “baseline” will be collected by the primary physician who is taking care of the participating patient. All subsequent visits will be over the phone with mother.](#) Telephone calls for follow up visit are expected to last 15 – 30 minutes.

Data analysis: interim and final

Final report: 2 months

Study procedure:

Suspected patient or patients with positive COVID results will be identified through Cerner. Patients will then be contacted through the primary physician to explain the study and obtain consent forms once accepted. The primary physician will then collect demographic and baseline data after obtaining patient consent (appendix 1 & 2). Apart from the initial visit, there is no anticipated future study visits. Data collection will be either through the phone or using a self-administered survey that will be sent through SMS.

The maximum follow-up period is 2 years. Based on the gestational age at time of enrolment might vary e.g. if the patient was enrolled early in pregnancy e.g. during the first trimester, the enrollment period will be for 2 years whilst patient who is enrolled in third trimester will be enrolled for less than 2 years.

During the follow up, patient will be contacted over the phone.

Further, we aim to collect data about psychological status i.e. depression and anxiety disorders using the depression Edinburgh Postnatal Depression Scale (EDPS) and the Generalized Anxiety Disorder 7 (GAD-7) surveys. Both surveys, the EDPS and GAD-7, are self-administered surveys that will be sent through an SMS link to the subject. In case patient was identified as having depression or anxiety disorder, the patient will be referred to contact the national mental health helpline at [name]. In case the study team is concerned about the mental health of the subject a direct referral will be sent through Cerner and psychiatrist will be consulted.

Informed Consent

a) *How people will be **NOTIFIED OR APPROACHED** to consider being a research subject in this study?*

Patient will be notified through:

1. Advertisements such as hospital posters and social media. In this case, filling the study online form will be considered as a patient consent.
2. Referral through the primary physician. In this case, the primary physician will explain the study to the patient and document her willingness to participate in Cerner.

b) *Describe the **CONSENT PROCESS** procedures (When, Where, How, by Whom).*

When an eligible patient is referred by her primary physician, a study coordinator will follow-up by phone to explain the study and obtain a verbal consent to release medical information. In case of self-referral, through filling the online form or calling the study coordinator, a study coordinator will follow with a phone call to explain the study and obtain a verbal informed consent.

c) *Describe **HOW LONG** potential participants will have to decide on participation.*

The patient will be given a 24-hour period to decide.

d) *Describe how subjects will be **SCREENED FOR ELIGIBILITY** for the study.*

Patients will be screened based on a confirmatory laboratory result of a positive SARS-CoV-2 PCR results.

e) *Describe how subjects will be **ENROLLED** into the research study below.*

Once the laboratory result is confirmed and verbal consent is obtained, patient details will be entered into the online study database and given a study number.

Risk

The is a prospective observational registry. There minimal risk of breach of patient confidentiality. To minimize this risk, data will be entered into an electronic registry software. The software will be secured with username and password and only accessible by the study investigators for data entry. Data extraction will only be accessible to study PIs and co-PIs. Paper based data collection sheet will be secured in locked cabinets accessible only by study PIs and co-PIs. Only de-identified data will be shared amongst investigators. If a breach in confidentiality occurs, the IRB will be notified immediately. Consent form containing the linking information between collected data and patient's identifiable information will be stored in a locked cabinet and/or password locked computer. Information on the password protected computer database will only be accessed by the investigators. Furthermore, the PI's office will remain locked. All study documentation will be stored according to the MRC guidelines

Bio-Specimens & Sample Collection

NA

Outcomes

We believe the results of this study will generate robust data. Prevalence of SARS-CoV-19 infection in pregnancy. Percentage and distribution of COVID-19 presenting sign and symptoms. Percentage of adverse pregnancy and neonatal outcomes. Description of mental status of pregnant women affected by COVID-19 infections.

Data Collection, Management & Confidentiality

a) Indicate below HOW study data will be collected for the proposed research.

Study Forms Study Database Study Web-Based/App Other

Please detail how study data will be coded:

Once informed consent is obtained, patient will be given study number and entered in the registry system. Data will be stored registry database/web-portal password protected on Cerner. Only study investigators have access for data entry. For follow up purposes, study investigators will have access to the identifiable information during the data collection period. No individual identity will be disclosed in results and publications.

b) Describe below WHERE and HOW the study data is physically stored.

In case paper-based document, such as signed informed consent, and CRFs, are used it will be stored in locked cabinets. Excel file containing patient identifiable information will be password protected. Electronic CRF (eCRF) will be developed by HMC Cerner team. The requirement for QPRECIOUS forms and feasibility has been discussed with HMC Cerner team (table 2). The forms will be stored on the patient's files with access control and confidential status to prevent form access and edit. This has already been discussed with HICT/Cerner team through [name], informatics lead at WWRC, coinvestigator in the study and Ob/Gyn consultant (below is the timeline of suggested milestones). For the purpose of this registry, the case report forms will be built in Cerner. The data will be store on central repository. The access of which will be controlled by the study PI and co-PI. To ensure the highest quality, the data will be reviewed by certain study members. The findings of this review along with other KPIs will be presented in the regular meeting of the study steering committee.

S. No	Activity	Owner	Comments
1.	Workflow finalization and users [nurses? Physician obgyn? who will fill the forms, when the forms are filled, which facilities it is used, Clinic setup required or not], to discuss with [name] – HICT CT team and SMEs	[name]/ [name]	To check with [name] availability for meeting
2.	Include RACS team and pursue their approval from Facility with in WWRC	[name] / [name] to discuss with RACS team on approval for forms to be designed	Share approvals with RACS document number for the forms
3	Log a change request in E service.hamad.qa	[name] / [name] interaction with [name]/ [name]/ [name]
4.	Review and analyze the forms	HICT Team	2 persons – 3 days tentative

5	Confirmation regarding the MRC approval for study	[name]/ [name]	
6	Building the forms on CERNER on CERT environment	Cerner	2 weeks
7	Validation of Forms on CERT environment	HICT and SMEs	3 days
8	Issue resolution and revalidation	Cerner- HICT	2 days
9	Building the forms on CERNER on PROD environment	Cerner	2 weeks
10	Validation of Forms on PROD environment – HICT and Team	HICT- SMEs	3 days
11	Go Live support	HICT	1 day

c) Describe below WHO controls access to the study data

Study PI and Co-PIs combined will control access to study data. Data access request must be written and signed by two members.

d) Describe below WHO has access to the study data.

Data entry level:

Data collection/entry: HMC physicians will be eligible to enter patient initial assessment form. Follow up data study investigators and research coordinators will have access to enter patient data into the database.

Data extraction for audit, analysis, report and request of collaboration:

Data extraction access will be granted to specified personnel designated by the register steering committee.

e) Describe below HOW the study data is accessed.

Level access will be employed from HMC Cerner team. Study data will be accessed using a dedicated username and password for specified members.

f) Will subject identifiers be shared outside of HMC? If YES describe below WHOM the study data is shared

No, only deidentified data will be shared.

Subject Withdrawal/ Withdrawal of Consent

In case patient wish to be withdrawn from the study, no further contact will be made. However, collected information up to the point of withdrawal will be included in the analysis. Subjects withdraw from the study will be asked whether they are willing to allow ongoing data collection and his response will be recorded.

9. Statistical Consideration and Data Analysis

Descriptive data: Numerical data will be presented as mean and standard deviation where normally distributed or median and range where it's not normally distributed. Categorical data

will be presented as frequency and percentages. Prevalence of COVID-19 will be calculated as total number of patients who were positive over total number deliveries in the same month. Inferential analysis will be used to assess association and tests will be selected according to suitability.

10. Adverse Event Reporting

This is an observation study. There are no anticipated adverse events.

11. Ethical Consideration.

The registry will only commence after obtaining approval from IRB/HMC in accordance with good clinical practice, and MoPH regulations

12. Sponsor, Funding & Collaborator Information

MRC

13. Dissemination of Results and Publication policy

Once the project is funded, the study team will initiate monthly meetings to discuss study plans and patient recruitment. Team leaders will also meet monthly to share study updates. Furthermore, the study results will be shared among peers in the department through presentation of study findings. Finally, once the study is completed, we aim to present our findings at the Hamad Medical Corporation Annual Research Day, local and international conferences and in peer-reviewed journals.

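### The COVID-19 symptom form is left off the GA 36 and GA 38 contacts, so women enrolled by about GA 30 have no scheduled symptom form between GA 34 and 6 weeks postpartum

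*Combined protocol and SAP*

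**What the plan says.** Objective 1.1 (section 4) is to "Study the course of COVID-19 disease i.e. its symptoms, duration, progression in pregnant women". The instrument for this after baseline is the "COVID-19 Symptoms Follow-up" row of Table 1 in section 6. It is marked for the four weekly contacts, GA 24, GA 34, 6 weeks postpartum, 6 months and 12 months, and is blank at GA 36 and GA 38. The "Pregnancy Status/Outcomes" row is marked at both of those contacts.

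Section 8 lists the gestational-age contacts again, "At 24 – 34 – 36 – 38 weeks of gestation", under the condition "provided that baseline and the 4 weekly follow up occurred earlier". The series that must come first is "weekly for 4 weeks".

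The calendar starts at diagnosis rather than at a fixed gestational age: section 6 states that "initial assessment will be done during the hospital admission up on COVID-19 diagnosis". COVID-19 questions at baseline sit on a separate form, "Demographics, Health History and COVID-19 Questions". The protocol gives no reason for omitting the symptom form at GA 36 and GA 38.

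**The concern.** GA 36 and GA 38 are the only follow-up contacts at which the woman is reached and the symptom form is not scheduled. For a woman diagnosed early enough, the last antenatal symptom form is at GA 34 and the next comes six weeks after birth. Symptoms that persist, return or first appear in the last weeks of pregnancy would then be recorded only in retrospect, if at all.

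The main aim in section 4 is the natural course of infection through pregnancy and the postnatal period, so knowing when late symptoms occurred has some value. Once the contact has passed, that timing can be recovered only from recall or clinical records.

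**Working it through.** The plan states no figure for this gap, so there is nothing to reproduce. The check builds each woman's contact calendar from the schedule.

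**Inputs from the protocol**
- Baseline at diagnosis, gestational age E (section 6).
- Weekly symptom forms at E+1 to E+4 (Table 1; section 8).
- GA 24, 34, 36 and 38 contacts only if they fall after the weekly series (section 8) and before delivery.
- Symptom form at GA 24 and GA 34, not at GA 36 or GA 38 (Table 1).
- Next symptom form 6 weeks after delivery (Table 1).

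**Assumption**
- Gestational age at delivery D is not given. I use 40 weeks, with a range of 37 to 41.

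**Formula**
- Gap = (D + 6) − L, where L is the gestational age at the last symptom form before delivery.
- Currently L = 34 if E + 4 ≤ 34, that is E ≤ 30. For later enrolment L = E + 4.
- With the form added, L becomes the later of E + 4 and the last of GA 36 or GA 38 reached before delivery.

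**Delivery at 40 weeks (6-week form at 46)**

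| Enrolled at GA | L now | Gap now | L with change | Gap with change |
|---|---|---|---|---|
| 30 or earlier | 34 | 46 − 34 = 12 | 38 | 46 − 38 = 8 |
| 31 | 35 | 11 | 38 | 8 |
| 32 | 36 | 10 | 38 | 8 |
| 33 | 37 | 9 | 38 | 8 |
| 34 | 38 | 8 | 38 | 8 |
| 35 | 39 | 7 | 39 | 7 |

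**Enrolled by GA 30, other delivery ages**
- D = 37: now 43 − 34 = 9; with change 43 − 36 = 7 (GA 38 is not reached).
- D = 39: now 45 − 34 = 11; with change 45 − 38 = 7.
- D = 41: now 47 − 34 = 13; with change 47 − 38 = 9.

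The number of symptom forms strictly between GA 34 and 6 weeks postpartum, for enrolment by GA 30 and delivery at 40 weeks, rises from 0 to 2. With delivery at 37 weeks it rises from 0 to 1.

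**Other gaps in the same row, for comparison**
- GA 24 to GA 34: 10 weeks.
- 6 weeks to 6 months postpartum: about 26 − 6 = 20 weeks.

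Neither of these contains a contact to which the form could be added. The gap from GA 34 contains two.

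**The case against.** The strongest reply is that the schedule follows diagnosis, and for the affected women the important part is already done. By GA 34 they have completed baseline and four weekly symptom forms. The outcomes in section 8 concern presenting signs and symptoms, which do not depend on GA 36 or GA 38. The depression and anxiety row of Table 1 also skips these two contacts, which fits a deliberate choice to keep late contacts short. The gap is close to the 10 weeks between GA 24 and GA 34 and shorter than the 20 weeks or so after the 6-week contact. Adding the form still leaves 8 weeks that span delivery. Finally, the follow-up forms are listed by title only in section 15, so the 6-week form may already ask about the whole interval.

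Most of this stands, and it rules out several stronger readings that a reader might infer:

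- **Symptom data thin out around delivery for everyone.** They do not. Women diagnosed after about GA 30 have weekly forms inside the window. Section 7 on sample size says that all cesarean deliveries are screened, so some diagnoses near birth are expected. For those women symptom contacts are densest around delivery.
- **Symptom percentages by stage of pregnancy are biased.** No such analysis is planned in section 8 or section 9, and Objective 1.1 names no stage of pregnancy.
- **Late pregnancy has no symptom coverage at all.** That depends on the recall period of a form that cannot be seen. If the 6-week form asks about everything since the previous contact, the interval is covered, though by recall.
- **Vertical transmission cannot be studied.** With delivery at 40 weeks, the women with the 12-week gap were diagnosed at least 10 weeks before birth. Women diagnosed near birth are already followed weekly, and neonatal COVID-19 status is collected directly.

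What the reply does not remove is that two calls are made in this interval without the form that every other follow-up contact carries, and no reason is given.

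**Conclusion.** The point holds as a minor improvement. For women enrolled at or before about GA 30, no symptom form is scheduled for 12 weeks when delivery is at 40 weeks, or 9 to 13 weeks for delivery at GA 37 to 41. The gap shortens by one week for each week of later enrolment from GA 31 to GA 33, and from GA 34 onwards the omission has no effect. The loss is confined to prospective timing of persistent, recurrent or new symptoms in late pregnancy.

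The sizes rest on the assumed delivery age and on contacts taking place on schedule. The protocol gives no distribution of gestational age at diagnosis, so the share of women affected cannot be stated. How much the gap matters also depends on the content of the 6-week form, which is not in the document.

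**What to change.** Mark the symptom form at GA 36 and GA 38 in Table 1. For women enrolled by about GA 30 this cuts the gap from 12 to 8 weeks with delivery at 40 weeks, and from 9–13 to 7–9 weeks over the assumed range.

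Because 8 weeks spanning delivery would remain, also check the 6-week postpartum form. Unless it already does so, have it record onset and end dates of symptoms since the last symptom contact, and whether onset was before or after delivery.

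The cost is a few more questions on two calls already planned, and possibly date fields on the 6-week form. No new contact is needed. If the short late contacts were intended, one sentence in section 6 giving the reason would be enough, with the date fields then carrying the late-pregnancy information.

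### The postpartum inclusion criterion does not tie infection to delivery, and no analysis rule keeps births completed before infection out of the pregnancy, neonatal and vertical-transmission percentages

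*Combined protocol and SAP*

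**What the plan says.** Section 7 lists three inclusion criteria. The first is "pregnant woman with suspected or confirmed SARS-CoV-2 infection". The second is "postpartum women who delivered during the last six weeks", with no infection condition and no timing. The third is "neonate(s) of women included in the registry", so babies of women admitted under the second criterion also enter. The sentence introducing the list names pregnant patients only: "We will include all pregnant patients with suspected or confirmed COVID-19 infection at all HMC facilities".

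Section 8 finds suspected or positive patients through Cerner. Items d and e under Informed Consent then screen and enrol on a positive PCR. Neither step refers to the date of delivery.

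The objectives in section 4 differ in scope among themselves. Objective 1 describes a registry "for women with suspected COVID-19 or confirmed SARS-CoV-2 in pregnancy and their neonates", and the justification is built on exposure in utero. The aim above it is wider: "The main aim of this study is to understand the natural course of the COVID-19 infection during pregnancy and postnatal period". Objective 1.2 reads "Study the pregnancy, postnatal and neonatal effect of COVID-19 disease", although its restatement in section 6 leaves out the postnatal part.

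The Outcomes paragraph of section 8 promises "Percentage of adverse pregnancy and neonatal outcomes. Description of mental status of pregnant women affected by COVID-19 infections", along with the prevalence of infection in pregnancy. Section 9 divides all positive patients by the deliveries in the same month. It defines no subset, stratum or denominator by timing of infection.

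**The concern.** Take a woman who delivers uninfected and first becomes infected five weeks later. She meets criterion 2, passes the PCR screen, and brings her baby in under criterion 3. Gestation at birth, stillbirth, growth restriction, birth weight, Apgar score and malformations were all settled before she was exposed, and in-utero transmission was impossible. Yet no rule keeps this pair out of the percentages of adverse pregnancy and neonatal outcomes.

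Three registry results are exposed:

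- **Adverse-outcome percentages.** Pairs whose outcome came before exposure carry background risk and pull the figures towards it. Miscarriage is pulled towards zero, because a woman who has delivered cannot miscarry that pregnancy.
- **Vertical transmission.** A baby infected at home by a mother infected after delivery could be tabulated as a possible vertical case.
- **Prevalence in pregnancy.** Infections acquired after delivery would inflate the numerator.

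What matters is the date of infection relative to delivery, not the date of enrolment. A woman infected in pregnancy but enrolled postpartum belongs in the pregnancy results.

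**Working it through.** **Text check.** Following the example woman through the plan:

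1. Section 7, criterion 2: eligible, since only the time since delivery is tested.
2. Section 8, items d and e: enrolled, since a positive PCR of any date suffices.
3. Section 7, criterion 3: her baby is enrolled.
4. Section 6, Table 1: pregnancy outcomes and neonatal outcomes are both scheduled at 6 weeks postpartum, with no separate schedule for infection after delivery.
5. Section 8 Outcomes and section 9: one registry-level percentage, with no restriction by timing.

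No step removes or separates her. The point rests on this sequence and needs no figure.

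**Illustration of size.** The plan gives no share of post-delivery infections and no outcome rates, so the inputs here are assumptions, apart from the six-week window (criterion 2) and the 170 to 200 cases per month (section 7, sample size).

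Assume constant infection hazard and constant detection over w weeks before delivery and 6 weeks after. The post-delivery share is f = 6/(w + 6):

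- w = 40: 6/46 = 13.0%
- w = 26: 6/32 = 18.75%, about 19%
- w = 12: 6/18 = 33.3%

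At 170 to 200 cases per month this is 22–26, 32–38 or 57–67 women per month. That scale is loose. The precision formula 1.96² × 0.15 × 0.85 / 0.05² gives 196, or 175 with a finite-population correction for 1,650. Both lie inside 170 to 200, whereas 15% of 1,650 is 248. The stated monthly figure may therefore be a precision sample size and not a case count.

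Pooled risk = (1 − f) × p1 + f × p0. With an assumed preterm risk of p1 = 15% after infection in pregnancy and p0 = 10% background:

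- f = 13.0%: 14.35%, a loss of 0.65 points
- f = 18.75%: 14.06%, a loss of 0.94 points
- f = 33.3%: 13.33%, a loss of 1.67 points

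The fraction of the excess that is lost equals f. With p0 = 10% and a true risk ratio of 2.0, the apparent ratio is 2 − f: 1.87, 1.81 or 1.67.

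**The case against.** The strongest reply is that the main aim and Objective 1.2 include the postnatal period, so postpartum cases are in scope. That stands. A reader might infer that criterion 2 contradicts the study's objectives and should be deleted. The documents do not support this: Objective 1 is narrower than the aim, and the two need reconciling. Criterion 2 can also be read as admitting women infected in pregnancy but identified after delivery, a group that must be kept.

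Second, no passage says that births will be attributed to a later infection. That also stands. The plan is silent, and the data forms (appendices 1 to 6) are listed but not reproduced, so they may record dates of diagnosis and delivery. Recording a date is not an analysis rule, however, and section 9 has none.

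Third, the effect may be small. At the 13% share the assumed shift is 0.65 points against the plan's 5-point margin of error, and 87% of the excess survives. It would be wrong to infer that any harm would be hidden. Uniform detection is also doubtful, since section 7 describes selective testing plus screening of all caesarean deliveries, which concentrates detection at delivery. But this shift is a bias, and enrolling more women does not shrink it.

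Fourth, a first positive test after delivery does not prove infection after delivery. Section 7 cites only 12% of positives as symptomatic. So it cannot be inferred that every positive infant of a woman first diagnosed postpartum was infected after birth.

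Finally, the mental-health consequence is minor. Sections 4 and 6 plan these measures in both periods and Table 1 schedules them by visit; only the Outcomes wording speaks of pregnant women alone.

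**Conclusion.** The point holds as a gap between a stated inclusion rule and a stated set of percentages. Criterion 2 specifies neither infection status nor its timing, and nothing later restricts pregnancy, birth, vertical-transmission or prevalence figures to infection before or at delivery. Followed literally, the plan permits biased figures against Objective 1, although it does not say that they will be produced.

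The direction is towards background rates for outcomes fixed at delivery, assuming that women infected later have background risk. The size cannot be determined from the documents. The 13% to 33% range depends wholly on the assumed weeks at risk and constant detection, and should be read as illustration, not estimate. The change should be made: the registry's main percentages are affected and the remedy is cheap.

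**What to change.** 1. Keep "postpartum women who delivered during the last six weeks" in criterion 2 and add the condition of suspected or confirmed SARS-CoV-2 infection, whether onset was in pregnancy or after delivery. This retains women infected in pregnancy but enrolled postpartum, and retains suspected cases. Reconcile Objective 1 with the main aim accordingly.
2. Classify each woman by date of symptom onset or first positive test against date of delivery: before or at delivery, after delivery, or timing uncertain. The last class would hold, for example, asymptomatic women first positive shortly after delivery; define its window in advance.
3. Restrict the primary pregnancy, birth and vertical-transmission percentages, and the numerator of prevalence in pregnancy, to infection before or at delivery. Add a sensitivity analysis that includes the timing-uncertain class.
4. Report postnatal-onset cases separately, for maternal course, mental health and later infant outcomes.

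The cost is one amended criterion, one derived variable and a short addition to section 9. PCR results are already sought through Cerner; symptom-onset dates may need a form field, which cannot be judged without the appendices. The pregnancy-outcome tables will have a somewhat smaller denominator, and some women's timing will stay unclassifiable.
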